Official title: Synergistic effect of ^{18}F -FDG PET radiomics and International Prognostic Index on outcome prediction in diffuse large B-cell lymphoma

NCT number: 04317313

Document date: July 29, 2021

Study Protocol and Statistical Analysis Plan

Background: Previous studies have shown that ¹⁸F-FDG PET radiomics is predictive of survival in DLBCL. However, to the best of the investigator's knowledge, a multi-feature radiomic signature for prognosis assessment of DLBCL has not yet been described. Furthermore, it remains unclear whether PET-based radiomics could add more prognostic values to the IPI in DLBCL.

Objectives: This study aims to develop ¹⁸F-FDG PET radiomic signatures, and investigate whether the RS could improve the prognostic value of the IPI in predicting progression-free survival (PFS) and overall survival (OS) in DLBCL.

Study design and methods:

Study population

We retrospectively included patients with newly-diagnosed DLBCL between July 2013 and July 2019 in our institution. The inclusion criteria were: 1) histopathologically confirmed DLBCL, 2) over 18 years old, 3) underwent pre-treatment ¹⁸F-FDG PET/CT, and 4) initial treatment with R-CHOP (rituximab, cyclophosphamide, doxorubicin, vincristine, and prednisone) or R-EPOCH (rituximab, etoposide, prednisone, vincristine, cyclophosphamide, and doxorubicin). Patients were excluded if they had coexistent central nervous system lymphoma or second primary cancer, underwent surgical resection, or had an incomplete follow-up.

Clinical variables including gender, age at diagnosis, cell of origin, performance status, B symptoms, Ann Arbor stage, serum lactate dehydrogenase level, serum β 2-microglobulin (β 2-MG) level, extranodal involvement and treatment regimens of each patient were recorded. The IPI score was calculated.

Patient Treatment and Follow-up

Patients were initially treated with standard first-line chemotherapy every 21 days. Response to treatment was assessed according to the Lugano classification.

Follow-up was performed every 3 months after the completion of treatment, and ended in July 2021. The endpoints included OS (defined as the period from the initial diagnosis to the death from any cause) and PFS (defined as the period from the initial diagnosis to the progression, relapse or death from any cause).

PET Image Segmentation and Feature Extraction

PET images were analyzed by two experienced nuclear medicine physicians who were blind to the patients' outcome. The volumes of interest (VOIs) were semiautomatically delineated using the LIFEx software (<https://www.lifexsoft.org/index.php>) with a fixed threshold of 41% SUVmax. A total of 1245 radiomic features were extracted via PyRadiomics software. The radiomics features consisted of four groups: (1) first-order statistics features; (2) shape descriptors features; (3) texture features calculated by gray level co-occurrence matrix (GLCM), gray level dependence matrix (GLDM), gray level run length matrix (GLRLM), and gray level size zone matrix (GLSZM); (4) filter and wavelet features obtained by filter and wavelet transformation of the original image, such as exponential, logarithm, square, square root and eight frequency band combinations (low-high-low [LHL], low-high-high [LHH], high-low-low [HLL], low-low-high [LLH], high-low-high [HLH], high-high-high [HHH], high-high-low [HHL] and low-low-low [LLL]).

Radiomics feature selection

First, intra-class correlation coefficients (ICCs) were used to evaluate the inter- and intra-observer agreement for 1248 features, including 3 conventional and 1245 radiomics features. Features with both inter- and intra-observer ICCs greater than 0.75 were retained. Then, the least absolute shrinkage and selection operator (LASSO) Cox regression algorithm with 10-fold cross-validation was applied to select the optimal features with non-zero coefficients in the training set. The radiomics signature was developed by linear combination of the selected features weighted by their respective coefficients. The cut-off value of the radiomics signature was identified by X-tile software. Based on the cut-off value of the R-signature, patients were divided into high-

and low-risk groups. Survival function of the R-signature was estimated by Kaplan-Meier analysis, and survival distributions were compared using log-rank test.

Model construction

Univariate Cox regression analysis was performed to investigate the prognostic value of the R-signature and clinical variables. Then, all significant variables were enrolled into a stepwise multivariate Cox regression to build an integrated radiomics-based model for PFS and OS prediction.

Model performance assessment

Time-dependent ROC curve analysis was conducted to investigate the predictive accuracy of the R-signature, clinical variables and the integrated radiomics-based model. The 95% confidence interval (CI) of the area under the curves (AUCs) were calculated by bootstrapping with 1000 resampling. The AUC between the radiomics-based model and clinical variables was compared by using the Delong's test. The calibration plots and the Hosmer-Lemeshow test were used to compare the predicted and observed probabilities of the radiomics-based model. The decision curve analysis (DCA) was applied to determine the clinical utility by quantifying the net benefits under different threshold probabilities in the whole cohort.

Statistical analysis

The chi-square test and independent *t*-test were performed using SPSS software (version 25.0, IBM). ICC, LASSO regression analysis, time-dependent ROC analysis, Delong's test, calibration plots, Hosmer-Lemeshow test, DCA and Kaplan-Meier survival analysis were performed using R software (version 3.6.1, <http://www.r-project.org>). A two-sided *P* value of < 0.05 was considered statistically significant.

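### Excluding patients for undefined incomplete follow-up selects on what happens after diagnosis; if it removes event-free losses and loss is non-informative, absolute PFS and OS risk is overestimated and same-cohort calibration cannot show it

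*Combined protocol and SAP*

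**What the plan says.** The cohort is retrospective: "We retrospectively included patients with newly-diagnosed DLBCL between July 2013 and July 2019 in our institution". Among the exclusions in Study population are patients who "underwent surgical resection, or had an incomplete follow-up". The document does not give a minimum duration, say whether PFS or OS status decides, cover the patient who has an event and is then lost, or state a censoring rule.

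Under Patient Treatment and Follow-up, "Follow-up was performed every 3 months after the completion of treatment, and ended in July 2021". Both endpoints start at initial diagnosis; for example, "PFS (defined as the period from the initial diagnosis to the progression, relapse or death from any cause".

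The analysis relies on methods that accept censored times: "Survival function of the R-signature was estimated by Kaplan-Meier analysis", with a log-rank comparison, Cox models and time-dependent ROC curves. Absolute risk is then used twice under Model performance assessment. For calibration, "The calibration plots and the Hosmer-Lemeshow test were used to compare the predicted and observed probabilities of the radiomics-based model". The decision-curve analysis works by "quantifying the net benefits under different threshold probabilities in the whole cohort". A training set is mentioned, but no cohort free of this exclusion is described.

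**The concern.** The other exclusions listed (central nervous system lymphoma, second primary cancer, surgical resection) do not depend on how long a patient was observed. This one does. On its natural reading, a patient who progresses at 8 months and then stops attending has a known PFS outcome and stays in. A patient who is progression-free at 8 months and then stops attending is removed. The retained cohort then holds too many events for the number of patients at risk.

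Kaplan-Meier, log-rank and Cox methods have no need of the exclusion, because a lost patient contributes time at risk until last contact. What is at stake is the absolute risk attached to the signature and the integrated model, and every result that uses it. Readers could not detect the error from the planned calibration, because predicted and observed risk would come from the same selected patients. They could not size it either, because the plan does not call for the excluded number to be reported.

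**Working it through.** The plan states no sample size, event count, survival rate or loss rate, so there is no figure of its own to reproduce. The check asks for direction and plausible size.

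**Inputs.** From the documents: diagnoses July 2013 to July 2019 and follow-up to July 2021, so potential follow-up A runs from 2 to 8 years. Assumed: even accrual (A uniform on 2 to 8), true 2-year PFS 70%, constant hazards, random loss of 2%, 5%, 10% or 20% by 2 years.

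**Two readings.** (A) Everyone lost event-free before July 2021 is dropped. (B) Only those lost event-free before 2 years are dropped. Both keep patients whose event came before loss.

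**Formulas, shown for 10% loss.**
- Event hazard λ = −ln(0.70)/2 = 0.1783 per year; loss hazard γ = −ln(0.90)/2 = 0.0527; s = λ + γ = 0.2310.
- Event within 2 years and before loss: (λ/s)(1 − e^(−2s)) = 0.7720 × (1 − 0.63) = 0.2856.
- Mean of e^(−sA): (e^(−2s) − e^(−8s))/(6s) = (0.6300 − 0.1575)/1.386 = 0.3409.
- Dropped under (A): (γ/s)(1 − 0.3409) = 0.2280 × 0.6591 = 0.150.
- No kept patient is censored before 2 years, so 2-year risk in the kept cohort is 0.2856/(1 − 0.150) = 0.336, and PFS reads 66.4%.
- Dropped under (B): 0.2280 × 0.37 = 0.084; risk 0.2856/0.9156 = 0.312, and PFS reads 68.8%.

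| Loss by 2 years | (A) dropped | (A) 2-year PFS | (B) dropped | (B) 2-year PFS | Censoring |
|---|---|---|---|---|---|
| 2% | 3.2% | 69.3% | 1.7% | 69.8% | 70% |
| 5% | 7.8% | 68.3% | 4.2% | 69.4% | 70% |
| 10% | 15.0% | 66.4% | 8.4% | 68.8% | 70% |
| 20% | 28.3% | 62.3% | 16.9% | 67.4% | 70% |

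**Other assumed rates.** With 5-year PFS 60%, 5-year OS 70% and 20% random loss by 5 years, reading (A) gives a 5-year PFS risk of 43.4% against 40.0%, and an OS risk of 33.0% against 30.0%. Censoring recovers the truth to within 0.1 point.

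**Calibration.** Take two independent standard-normal predictors (IPI and R-signature, log hazard ratio 0.5 each) and fit a Cox model to the patients kept under (A). Observed over predicted 2-year risk in all patients is 0.98, 0.95, 0.91 and 0.82 across the four loss rates. In the kept cohort it is 1.00 throughout.

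**Discrimination.** In the same set-up the AUC gain over the IPI is 0.064 in truth and 0.064 to 0.062 under (A). If the loss hazard also changes 2.2-fold per SD of risk (5% to 10% loss), the gain is 0.058 to 0.070 and the R-signature hazard ratio 1.56 to 1.72, against 1.65.

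**Decision curve.** At a 30% threshold, treat-all net benefit is p − (1 − p) × 0.3/0.7. At 10% loss the kept-cohort event risk p is about 0.338, giving 0.338 − 0.662 × 0.4286 = 0.054, against 0.000 with no loss. The model's raw value rises from 0.094 to 0.124, so its advantage over the best default falls from 0.094 to 0.070. At 20% loss the advantage is 0.047. At thresholds of 40% and 50% it rises instead, from 0.057 to 0.077 and from 0.032 to 0.044 at 10% loss.

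**Informative loss (10% lost by 2 years, event hazard raised after loss).** PFS as truth / exclusion (A) / censoring:
- Hazard doubled: 2 years 68.9 / 66.4 / 70.0%; 5 years 37.7 / 37.0 / 41.0%.
- Hazard fourfold: 2 years 67.3 / 66.4 / 70.0%; 5 years 34.7 / 37.0 / 41.0%.

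Exclusion is nearer the truth in three of these four cases, and in the last it errs in the other direction. At 5 years it reads 37.0% whether the truth is 41.0% (no change in hazard), 37.7% or 34.7%.

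**Another reading.** A 2-year minimum that also removes earlier events would make 2-year PFS 100% and 5-year PFS 59%, against a true 41%.

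**The case against.** The strongest reply is that the text supports only an undefined criterion. The bias needs three further conditions: event-free losses dropped while earlier events are kept, loss unrelated to prognosis, and a loss rate that matters. At 2% to 5% loss the shift in 2-year PFS is under 2 points. If the term means only patients never seen again after diagnosis, for reasons unrelated to prognosis, there is little or no problem. Under informative loss, censoring can be further from the truth than exclusion. The stated objective, whether the signature adds to the IPI, is barely affected.

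All of that stands as a limit on the claim. It does not remove the point: on its natural reading the stated rule selects on outcome, and only a definition and the restored patients can show which case applies.

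A reader might infer three stronger things that the documents do not support.
- That the exclusion inflates the model's clinical utility. Raw net benefit rises in the selected cohort, but so does treat-all, and the model's advantage falls or rises according to the threshold.
- That it exaggerates the gain over the IPI. The AUC gain and hazard ratios hardly move under random loss, and can move either way if loss depends on risk.
- That patients were dropped to suit the Hosmer-Lemeshow or DeLong procedures. The plan gives no reason for the exclusion.

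The missing prediction horizon, and how those two procedures handle censoring, are separate matters.

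**Conclusion.** The concern holds in conditional form. The criterion is undefined and uses information from after the time origin. If it removes event-free losses, keeps earlier events, and loss is non-informative, absolute PFS and OS risk is overestimated and calibration within the cohort is blind to it. Under the assumptions shown, the error in 2-year PFS runs from less than 1 point to about 8 points under reading (A), and from a fraction of a point to under 3 points under (B). The true size cannot be known from the documents, and other readings or informative loss can change the direction. This should be corrected because calibration and decision-curve analysis depend on absolute risk, but it does not undermine the comparison with the IPI. Confidence is moderate, since the meaning of the term is not given.

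**What to change.** Remove incomplete follow-up as an exclusion. Include every otherwise eligible patient with any contact after diagnosis, censoring OS at the date last known alive and PFS at the last progression-free assessment. Exclude only patients with no post-diagnosis contact, say so in the text, and report their number and baseline IPI factors. Show the main results with and without the restored patients.

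Do not rely on censoring alone. Add a sensitivity analysis for informative loss, for example by imputing events after loss with the hazard multiplied by 1, 2 and 4. In the 10%-loss example this gives 5-year PFS of 41.0%, 37.7% and 34.7%, so the dependence on the assumption is visible. The multipliers are illustrative and should be fixed before the analysis is rerun.

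**Cost.** The work uses existing records, pre-treatment scans and readers, with no new patient procedure. The added scans must be segmented, and the ICC filter, LASSO, X-tile cut-off, Cox models and performance measures rerun, so the signature itself may change. If the scans cannot be segmented, report the number, event status and baseline features of those excluded, and limit absolute-risk and calibration claims to the selected cohort.

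### The planned comparison can show that PET adds to the IPI but cannot separate radiomics from the three conventional PET measures, because no IPI + conventional PET model is planned

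*Combined protocol and SAP*

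**What the plan says.** The Background section gives the gap to be filled: "it remains unclear whether PET-based radiomics could add more prognostic values to the IPI in DLBCL". The Objectives section asks whether the radiomic signature improves the prognostic value of the IPI for PFS and OS.

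The section on segmentation and feature extraction reports that "A total of 1245 radiomic features were extracted via PyRadiomics software". The section on radiomics feature selection then adds three further measures and evaluates "inter- and intra-observer agreement for 1248 features, including 3 conventional and 1245 radiomics features". One filter applies to all of them: "Features with both inter- and intra-observer ICCs greater than 0.75 were retained". The LASSO Cox step follows directly and "was applied to select the optimal features with non-zero coefficients in the training set". No step sets the conventional measures aside. Finally, "The radiomics signature was developed by linear combination of the selected features weighted by their respective coefficients".

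On the comparator side, the Study population section begins its list with "Clinical variables including gender, age at diagnosis, cell of origin, performance status, B symptoms, Ann Arbor stage, serum lactate dehydrogenase level" and continues with laboratory, extranodal and treatment items, plus the IPI. It names no PET measure. Model construction considers the signature and the clinical variables. Model performance assessment uses time-dependent ROC to "investigate the predictive accuracy of the R-signature, clinical variables and the integrated radiomics-based model", and the DeLong test sets the radiomics-based model against the clinical variables.

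**The concern.** The plan's own wording makes the three conventional measures something other than radiomics, yet they may become part of what is called the radiomics signature. They are also missing from the benchmark. The two arms of the planned comparison thus differ by all the PET information at once, conventional and radiomic.

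At stake is the interpretation of a positive result. If the prognostic content lies in information that a conventional PET measure already carries, the planned analysis would still show a gain over the IPI, and the title and objective would lead readers to credit it to radiomics. The plan contains no result that would tell them otherwise.

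**Working it through.** **1. The plan's own figure.** 3 conventional + 1245 radiomic = 1248, which reproduces the stated pool. The conventional share is 3/1248 = 0.24%. The documents give no sample size, event count or effect size, so nothing else can be reproduced.

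**2. What each planned analysis contains.**

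| Step | Conventional PET measures |
|---|---|
| ICC filter | included, pooled with the radiomic features |
| LASSO selection | eligible if retained by the filter |
| Clinical variable list | not named |
| Univariate and stepwise Cox | only through the signature, if selected |
| Time-dependent ROC, DeLong | only through the signature, if selected |

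No listed model contains the IPI with conventional PET and without the signature. Nor is a signature built only from the 1245 radiomic features planned.

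**3. Does the missing comparator matter? An illustration; every input is assumed.**
- The IPI takes values 0 to 5 (log HR 0.35 per point). One conventional measure V has log HR 0.6 per SD and a built-in association of about 0.4 with the IPI.
- There are 40 radiomic features with zero true effect; 20 of them correlate with V at rho = 0.6 or 0.9.
- LASSO Cox at one fixed penalty runs on the joint pool of V and the 40 features. Training N is 150 or 300, about 37–38% have events, and an independent test set of N/2 is used, with 100 replicates.
- Gain over IPI = C(IPI + signature) − C(IPI). Gain over conventional PET = C(IPI + signature) − C(IPI + V).

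| N | rho | Radiomic log HR | C: IPI | C: IPI + signature | C: IPI + V | Gain over IPI | Gain over IPI + V | V selected |
|---|---|---|---|---|---|---|---|---|
| 150 | 0.6 | 0 | 0.705 | 0.726 | 0.742 | +0.021 | −0.017 | 95% |
| 150 | 0.9 | 0 | 0.705 | 0.732 | 0.742 | +0.027 | −0.010 | 25% |
| 300 | 0.6 | 0 | 0.703 | 0.738 | 0.742 | +0.035 | −0.004 | 100% |
| 300 | 0.9 | 0 | 0.703 | 0.739 | 0.742 | +0.035 | −0.003 | 67% |
| 300 | 0.6 | 0.6 (one independent feature) | 0.693 | 0.759 | 0.728 | +0.066 | +0.031 | 100% |

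Differences were taken before rounding, so two differ by 0.001 from the rounded columns.

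The gain over the IPI is positive in every row, whether or not radiomics carries information of its own. Only the gain over IPI + V changes sign. The second row also shows that pooling is not the whole cause: V was selected in 25% of replicates, yet the signature still beat the IPI through features correlated with V.

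**4. Limits.** The simulation uses one conventional measure instead of three, 41 candidates instead of 1248, no ICC filter and a fixed penalty. It compares the pooled signature with V. It does not fit the full nested model proposed under the fix.

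**The case against.** The strongest reply is that the objective is met as written. It asks whether the signature improves the IPI, the signature's construction is disclosed, and a gain may fairly be credited to the PET-derived signature as a whole. First-order and shape features are radiomic by the plan's definition, so information on uptake and lesion geometry is already inside the radiomic set. Pooling is also defensible, since it lets simple measures compete with complex ones and the coefficients show which won. All of this stands. What it does not supply is support for crediting radiomics specifically, over PET measures that the plan itself calls conventional.

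Three stronger readings are tempting, and the documents do not support them.

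- **That conventional measures make up or dominate the signature.** They enter only if they pass ICC > 0.75 and LASSO selects them. Even their entry to LASSO is the natural reading of the sequence, not an explicit statement. Removing them from the pool would not by itself cure the problem, as the second row of the table shows.
- **That a gain over the IPI would be unrelated to radiomics, by some forecastable amount.** A zero radiomic effect was an input to the first four rows, not a finding. The three measures are not named, and no N or effect size is given.
- **That failing to beat IPI + conventional PET would prove radiomics adds nothing.** In a check with assumed inputs (binary outcome, about 36% events, log-OR 0.5 each for the IPI and V, and a radiomic feature correlated 0.6 with V with its own log-OR of 0.6 per SD), the DeLong test on held-out patients detected the true increment in about 11% of runs (150 training, 75 test) and 21% (300 and 150). At log-OR 0.3 the figure was 3–8%. A null result in cohorts of that size says little.

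**Conclusion.** The concern holds in a limited form. The planned contrast can establish that PET-derived information adds to the IPI; it cannot separate radiomics from conventional PET measures, and the stated gap concerns radiomics. This follows from which models the plan lists and does not depend on any simulation.

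The gains of 0.021 to 0.035 in C-index with no radiomic effect illustrate the mechanism under assumed inputs and do not estimate the result of this study. The size here cannot be calculated from the documents. The main gap is the missing comparator; pooling is secondary. It does not invalidate the study. It limits what a positive result can be said to mean, and an inexpensive added analysis can address it.

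**What to change.** For PFS and for OS, add a nested comparison in the same validation data:

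- (a) IPI;
- (b) IPI + the 3 conventional measures;
- (c) IPI + the 3 conventional measures + a signature built from the 1245 radiomic features only.

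Name the three measures. Report the (c) minus (b) difference in discrimination with a 95% CI; the 1000-resample bootstrap already planned for the AUCs can be applied to the paired difference.

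State the interpretation in advance. Credit a gain to radiomics specifically only if (c) versus (b) supports it. Otherwise, where the data show a gain over the IPI, say that the PET-derived signature improves the IPI and that an added contribution of radiomics beyond conventional PET was not shown, without concluding that it is absent.

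The cost is one extra LASSO fit and two extra Cox models per endpoint. The conventional measures are already in the agreement analysis, so no new patients or imaging are needed. The downside is that the reported radiomics gain may shrink.

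### Tuning the LASSO Cox by an unrepeated 10-fold cross-validation leaves the selected features partly dependent on the fold seed; averaging over repeated partitions under a stated lambda rule would be steadier

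*Combined protocol and SAP*

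**What the plan says.** Under 'Radiomics feature selection', the combined protocol and SAP first assesses observer "agreement for 1248 features, including 3 conventional and 1245 radiomics features". It then filters: "Features with both inter- and intra-observer ICCs greater than 0.75 were retained". The number that passes is not given. What passes goes into a "least absolute shrinkage and selection operator (LASSO) Cox regression algorithm with 10-fold cross-validation", which "was applied to select the optimal features with non-zero coefficients in the training set". The selected features become the signature directly: "The radiomics signature was developed by linear combination of the selected features weighted by their respective coefficients".

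The feature list under 'PET Image Segmentation and Feature Extraction' includes "filter and wavelet features obtained by filter and wavelet transformation of the original image", so many candidates are re-expressions of one another.

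The plan names no seed, number of repeats, stratification of folds by event, lambda rule (the minimum of the cross-validation curve, or the one-standard-error choice) or action if no feature is selected. It gives no training-set size or event count. The only other resampling is under 'Model performance assessment', where AUC confidence intervals "were calculated by bootstrapping with 1000 resampling". Nothing there says that the feature selection is repeated within the bootstrap.

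**The concern.** K-fold cross-validation assigns patients to folds at random. With many correlated candidates and limited events, the cross-validated deviance curve can be flat near its minimum, so a different assignment can move the chosen lambda and with it the features kept and their weights. The X-tile cut-off, the Kaplan-Meier groups, the Cox models, the AUCs, the calibration and the decision curves all use that signature and so inherit the one draw.

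The study aims at both PFS and OS. By the plan's definitions every death is also a PFS event, so a signature fitted to OS has no more events than one fitted to PFS and is no better protected.

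At stake is how far the study's central product reflects the data and how far an unrecorded random choice.

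**Working it through.** **Inputs from the plan.** Candidate features before the ICC filter: 3 + 1245 = 1248, which matches the plan's total. This is an upper bound on what LASSO receives. Method: LASSO Cox, 10-fold cross-validation, training set only.

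**Inputs assumed, because the plan gives none.** Training-set size, events, correlation and effect size. The main simulation used 150 or 250 patients, 63 to 116 events, and blocks of 24 features with within-block correlation 0.7. The signal acted through 3 latent factors with log hazard ratio 0 (null), 0.3 (weak), 0.5 (moderate) or 0.8 (strong). One scenario used 600 features to mimic the ICC filter.

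**Procedure.** Six scenarios, 7 data sets each (6 × 7 = 42), 60 fold seeds per data set. Within a data set only the seed changed. For each data set, range = largest minus smallest number of selected features over the seeds. 'Mixed' means that some seeds selected no feature and others at least one. Example, weak signal at lambda-min: (10 + 25 + 21 + 34 + 13 + 21 + 10) / 7 = 134 / 7 = 19.1.

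| Scenario | Mean range, lambda-min | Data sets with range of 10 or more | Mixed, lambda-min | Mixed, lambda-1SE |
|---|---|---|---|---|
| Null, n=150, p=1248 | 15.4 | 5/7 | 6/7 | 0/7 (always empty) |
| Weak, n=150, p=1248 | 19.1 | 7/7 | 4/7 | 3/7 |
| Moderate, n=150, p=1248 | 14.4 | 5/7 | 0/7 | 5/7 |
| Moderate, n=250, p=1248 | 15.6 | 6/7 | 0/7 | 5/7 |
| Moderate, n=150, p=600 | 11.9 | 4/7 | 1/7 | 4/7 |
| Strong, n=250, p=1248 | 16.6 | 6/7 | 0/7 | 0/7 |

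The lambda-min count moved with the seed in 41 of 42 data sets, and by 10 or more in 5 + 7 + 5 + 6 + 4 + 6 = 33. These ranges compare the extremes of 60 seeds; two seeds taken at random will usually differ by less.

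**Checks in other settings (all inputs assumed).**
- cv.glmnet, one weak-signal data set with 65 events, 20 seeds: lambda-min gave 0 to 3 features and was empty for 5 seeds; lambda-1SE was empty for all 20.
- cv.glmnet, n=140, p=600, 51 to 65 events: the lambda-min count ran, for example, from 10 to 23 in one data set and from 0 to 6 in another.
- n=150, p=400, about 78 events, 12 data sets × 12 seeds: ranges such as 5 to 14, 6 to 23, 12 to 37 and 0 to 15. In the steadier data sets the count hardly moved. Jaccard overlap of the selected sets was 0.60 to 0.96.
- n=120, p=1000, about 45 events, two weak signal strengths, 25 data sets × 8 seeds each: 52% of data sets were mixed. On average 5% of patients changed side of the median score (0.05 × 120 = 6 patients), and 10% for the worst pair of seeds (12 patients).

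**Effect of averaging.** Averaging the curve over 20 partitions before taking lambda-min gave mean ranges, in table order, of 0.3, 2.9, 0.9, 0.6, 0.4 and 1.9. Those ranges cover 3 replicates against 60 for single partitions, so the two are not like for like. A like-for-like comparison of three draws in the n=140 setting, averaging only 8 partitions, cut the range from about 0.4–6.0 features to 0–3. One weak data set still gave 0, 8 and 10 features after averaging over 20 partitions.

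**The case against.** Unrepeated 10-fold cross-validation is a valid way to tune a LASSO, and the count of selected features is a poor measure of harm: correlated features can replace one another with little change in the score. The patient-level shift was only about 5%, in a weak-signal setting, and was measured at the median, whereas the plan cuts at an X-tile value. This stands, and it limits how serious the point is.

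A reader might infer four stronger things that the documents do not support:

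- *That LASSO was run on 1248 features.* That is the count before the ICC filter. The run with 600 features showed the same instability, so the point survives the correction.
- *That a single partition was certainly used.* This is inferred from silence on repeats; it is the plain reading, not a stated fact.
- *That the seed decides in general whether a signature exists.* At lambda-min this was mainly a null- or weak-signal result. At lambda-1SE it extended to a moderate signal. It did not occur in the strong-signal scenario under either rule. The plan states neither the rule nor enough about the data to say which case applies.
- *That the seed biases the study towards a positive result, or that the signature cannot be reproduced.* No effect on AUC, hazard ratio, decision curves or false-positive rate was computed. A recorded seed makes the fit repeatable on the same data, and a published formula can be applied by anyone. Nothing in the documents suggests that a seed was chosen for its result.

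**Conclusion.** The point holds as a worthwhile, inexpensive improvement and does not invalidate the approach. It goes beyond missing detail, because following the text as written gives a signature that depends partly on the fold assignment, and a steadier procedure is available. Under the assumed conditions the number of features usually moved with the seed and often by 10 or more between extreme seeds. An empty signature under some seeds only is a real possibility if the signal is weak, or if it is weak to moderate and the one-standard-error rule was used. The demonstrated effect on risk grouping is modest. All the ranges rest on assumed sample size, events, correlation and effects; they illustrate the mechanism and do not estimate its size in this cohort.

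**What to change.** In the training set, repeat the 10-fold cross-validation (for example 100 times, with listed seeds and folds stratified by event), average the deviance curves, and choose lambda once from the averaged curve by a rule fixed in advance, stating whether it is lambda-min or lambda-1SE. Report each feature's selection frequency over the repeats. If the averaged curve selects no feature, report that no signature was found. Also state the number of ICC-retained features and the training-set size and events, so that a reader can judge the exposure. If the analysis is already complete, run this as a sensitivity analysis.

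The cost is minutes of computing and a short addition to the plan. The downside is that the signature may have fewer features or none. Averaging reduces the seed dependence but does not fully remove it when the signal is weak, and 100 repeats were not themselves tested here; that is why the selection frequencies should be shown.
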